4.3 Number of Patients

A total of 40 evaluable patients will be enrolled in this study with 20 patients randomized to each arm: 20 patients will receive celecoxib and 20 patients will receive placebo. It is expected that 25% of patients who start study therapy and undergo surgery will not start adjuvant radiation. Patients who do not start adjuvant radiation will be replaced. Taking this into account, it is estimated that 53 patients will be randomized to result in 40 evaluable patients.

4.4 Number of Study Centers

This will be a single-center trial run at the Huntsman Cancer Institute at the University of Utah.

4.5 Study Duration

Based on current volumes, it is proposed that this study can be completed within 2 years of initiation.

5 ELIGIBILITY CRITERIA

This eligibility checklist is used to determine patient eligibility and filed with the enrolling investigator's signature in the patient research chart.

Patient No. _____

Patient's Initials: (L,F,M) _____

5.1 Inclusion Criteria

Yes/No (Response of "no" = patient ineligible)

5.1.1 _____ Male or female subject aged ≥ 18 years.

5.1.2 _____ Advanced-stage (overall stage III and IV) head and neck cancers (sinonasal oral cavity, oropharynx, larynx, and hypopharynx) undergoing surgical resection and then adjuvant radiation. Primary and recurrence cases are acceptable.

5.1.3 _____ Karnofsky Performance Status of ≥ 70 .

5.1.4 _____ Adequate organ function demonstrated on labs drawn during the screening window and defined as:

- Hematologic:
 - Hemoglobin ≥ 10 g/dL
- Hepatic:
 - Total Bilirubin ≤ 2 mg/dL
 - AST(SGOT)/ALT(SGPT) $\leq 2.5 \times$ institutional ULN
 - Albumin > 3.5 g/dL
- Renal:
 - eGFR ≥ 30 mL/min/1.73m² or creatinine clearance ≥ 30 mL/min by Cockcroft-Gault:
 - Males:
$$\frac{(140 - \text{age}) \times \text{weight}[kg]}{\text{serum creatinine } \left[\frac{mg}{dL} \right] \times 72}$$
 - Females:
$$\left(\frac{(140 - \text{age}) \times \text{weight}[kg]}{\text{serum creatinine } \left[\frac{mg}{dL} \right] \times 72} \right) \times 0.85$$
 - Serum potassium within normal limits.

- 5.1.5** _____ Negative serum or urine pregnancy test at screening for women of childbearing potential.
- 5.1.6** _____ Highly effective contraception for female subjects throughout the study and for at least 5 days after the last dose of study therapy if the risk of conception exists (see [section 8.6](#)).
- 5.1.7** _____ Recovery to baseline or \leq Grade 1 CTCAE v5.0 from toxicities related to any prior treatments, unless AE(s) are clinically nonsignificant and/or stable on supportive therapy.
- 5.1.8** _____ Willing to maintain a diary of all opioids used during the trial for the treatment of pain.
- 5.1.9** _____ Able to provide informed consent and willing to sign an approved consent form that conforms to federal and institutional guidelines.
- 5.1.10** _____ Subject has verbally confirmed they are willing to complete adjuvant radiation therapy if recommended after surgery per protocol.
- 5.1.11** _____ Adjuvant radiation has been recommended by the institutional treatment planning conference with the best available data, but will be confirmed based on final surgical pathology.

5.2 Exclusion Criteria

Yes/No (Response of “yes” = patient ineligible)

5.2.1 _____ Known distant metastatic disease or the tumor is deemed not surgically resectable.

5.2.2 _____ Established in a pain management clinic or has taken opioids regularly for ≥ 6 months.

5.2.3 _____ Known or suspected to be poor CYP2C9 metabolizers based on previous history/experience with other CYP2C9 substrates (such as warfarin, phenytoin).

5.2.4 _____ Known hypersensitivity to celecoxib, aspirin, other NSAIDs, or sulfonamides.

5.2.5 _____ Uncontrolled hypertension defined as blood pressure (BP) > 150 mmHg systolic or > 90 mmHg diastolic on three consecutive reads, taken in one sitting, despite optimal antihypertensive treatment.

5.2.6 _____ Patients with a known history of the following:

- Cerebrovascular accident (CVA), stroke, or cardiovascular thrombotic events (e.g. acute myocardial infarction).
- Chronic heart failure.
- Gastrointestinal bleeding, ulceration, peptic ulcer disease, or perforation of the stomach or intestines.
- Aspirin-sensitive asthma.
- Chronic kidney disease, stage 4 or 5.

5.2.7 _____ Patients with a prior or concurrent malignancy whose natural history or treatment has the potential to interfere with the safety or efficacy assessment of the investigational regimen

5.2.8 _____ The subject has an uncontrolled, significant intercurrent or recent illness requiring systemic therapy, would preclude safe study participation, or is deemed clinically significant by the investigator.

5.2.9 _____ Known HIV infection with a detectable viral load within 6 months of the anticipated start of treatment.

Note: Patients on effective antiretroviral therapy with an undetectable viral load within 6 months of the anticipated start of treatment are eligible for this trial.

5.2.10 _____ Known chronic hepatitis B virus (HBV) or hepatitis C virus infection with a detectable viral load.

Note: Patients with an undetectable HBV viral load on appropriate suppressive therapy are eligible. Patients with an undetectable HCV viral load on appropriate treatment are eligible.

Short Title: RESILIENCE

Version Date: 18APR2023

5.2.11 _____ Subjects taking prohibited medications as described in Section 7.3.2. A washout period of prohibited medications for a period of at least 5 half-lives or as clinically indicated should occur prior to the start of treatment.

I certify that this patient meets all inclusion and exclusion criteria for enrollment onto this study.

5.3 Recruitment Strategies

Potential patients will be identified by Head and Neck Investigators in the setting of their outpatient clinics.

6 STRATIFICATION FACTORS

At the time of randomization, patients will be stratified by the treating provider.

7 TREATMENT PLAN

7.1 Administration Schedule

Celecoxib 200 mg/20 mL or placebo will be taken orally or by feeding tube twice daily (every 12 hours \pm 2 hours) without regard to food. Patients will complete 1 to 7 day(s) of study therapy prior to surgery and continue regular dosing until the completion of radiation therapy.

7.2 Celecoxib/ Placebo

7.2.1 How Supplied, Stored, Packaged and Labeled

Celecoxib/placebo will be compounded by Investigational Drug Services at Huntsman Cancer Institute into an oral suspension. The content of celecoxib will be suspended with Ora-Blend, a suspending and flavoring agent, as described by Donnelly et al to a final concentration of 10 mg/mL.¹¹ The suspension will be stored and dispensed in amber PVC bottles.

Placebo will be provided as assigned and will be identical in appearance to match their active counterparts.

Celecoxib/placebo will be kept at the Huntsman Cancer Institute Investigational Pharmacy in accordance with Good Clinical Practice (GCP) and GMP requirements and will be inaccessible to unauthorized personnel. Celecoxib/placebo suspension is stable for 93 days when refrigerated or stored at room temperature. The suspension should be stored in a well-ventilated area at 5-25°C. Investigators or designated personnel should check the temperature of the storage room daily and ensure that temperature monitoring devices are working correctly.

7.2.2 Preparation and Administration

Subjects will be provided enough celecoxib to last until their next scheduled visit. Celecoxib 200 mg/20mL should be administered orally or by feeding tube without regard to food twice daily (every 12 hours \pm 2 hours). It should not be coadministered with aluminum or magnesium-containing antacids. Subjects should not take extra medication for any reason nor should they re-administer in the case of vomiting after administration. If a dose is missed outside of the dosing window, it should not be made up.

7.2.3 Accountability and Compliance

Drug compliance will be recorded by patients on the drug diary (see Appendix 2). A member of the study team will review patient drug compliance at the end of treatment for each cycle and provide patient re-education as required. At the discretion of the principal investigator, a subject may be discontinued from the trial for non-compliance with study visits or study drug.

Excess or unused study drug should be returned to the investigative site, for accounting and destroyed in accordance with GCP after drug accountability has been performed.

7.3 Concomitant Medications and Therapies

7.3.1 Allowed Therapy

Any medication which is considered necessary for a subject's welfare is permitted and may be given at the discretion of the investigator. Medications for the treatment of underlying disease and symptomatic treatment of adverse events are permitted. Exceptions are listed in the section below.

7.3.2 Prohibited Therapy

Prohibited therapies that are necessary for patient health and wellbeing may be allowed only after discussion with and approval from the principal investigator and the medical monitor (and the DSMC when applicable).

Celecoxib is primarily metabolized by CYP2C9 in the liver. Co-administration of celecoxib with drugs that are known to inhibit CYP2C9 should be done with caution. Significant interactions may occur when celecoxib is administered together with drugs that inhibit CYP2C9. In vitro studies also indicate that celecoxib is an inhibitor of CYP2D6. Therefore, there is a potential for an in vivo drug interaction with drugs that are metabolized by CYP2D6.

In addition to cautionary use of CYP2C9 inhibitory drugs and those metabolized by CYP2D6, the following medications are prohibited while on study therapy unless prior approval is obtained:

- Other NSAIDs (e.g. ibuprofen, naproxen, etc.)
 - Aspirin may be administered post-surgery but should be administered with caution.
- Anticoagulants (e.g., warfarin)
- Known inhibitors of CYP2C9 (e.g., fluconazole)
- Warfarin
- Lithium
- Thiazides, loop diuretics, ACE-inhibitors, or angiotensin II antagonists

Celecoxib should not be coadministered with aluminum- or magnesium-containing antacids, but such antacids may be taken two hours after celecoxib dosing.

7.3.3 Duration of Therapy

Subjects will receive twice-daily dosing of 200 mg celecoxib three to seven days prior to surgery and continue twice-daily dosing until the completion of adjuvant radiation. The total duration of treatment should be approximately four to six months.

Subjects will receive celecoxib treatment until intolerable toxicity, completion of adjuvant radiation, or six months.

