| Study Center | Single Site: Huntsman Cancer Institute |
| Objectives | 
Primary Objective: To assess the number of days from surgery to the initiation of radiation with the addition of celecoxib compared to placebo.
 
Secondary Objectives:
 
 - To assess overall pain control and management for patients on celecoxib compared to placebo. - To assess functional outcomes for patients on celecoxib compared to placebo. - To assess the effect of celecoxib therapy on Quality of Life (QoL) compared to placebo. - To assess the average number of treatment days missed during adjuvant radiation for patients on celecoxib compared to placebo. |
| Number of Subjects | 60 |
| Diagnosis and Main Eligibility Criteria | 
Inclusion Criteria:
 
 - Advanced-stage (overall stage III and IV) head and neck cancers (sinonasal, oral cavity, oropharynx, larynx, and hypopharynx) undergoing surgical resection and then adjuvant radiation. - Karnofsky Performance Status of ≥ 70 - Adequate organ function. 
Exclusion Criteria
 
 - Metastatic disease - Exclude patients with chronic kidney disease (stage 4 and 5), prior CVA or acute MI, chronic heart failure, prior episode of GI bleed or stomach or intestinal ulcer, and liver failure. |

Short Title: RESILIENCE

Version Date: 18APR2023

| | |
|-------------------------------------|---|
| | 
- Uncontrolled hypertension- Established in a pain management clinic or has taken opioids regularly for \geq 6 months. |
| Study Product, Dose, Route, Regimen | Celecoxib/placebo 200mg BID oral or via a feeding tube |
| Duration of administration | Celecoxib/placebo will be taken 1 to 7 days prior to surgery until the completion of adjuvant radiation, approximately 4 months total, maximum allowable time on the study is limited to 6 months. |
| Reference therapy | Placebo |
| Statistical Methodology | A mixed-effects regression model that accounts for clustering (patients nested within providers) to compare the average number of days from surgery to the initiation of radiation between treatment and control groups |

SCHEMA

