3.1.2 Physical and Chemical Properties

Celecoxib is chemically designated as 4-[5-(4 methylphenyl)- 3-(trifluoromethyl)-1H-pyrazol-1-yl] benzenesulfonamide and is a diaryl-substituted pyrazole. The empirical formula is C17H14F3N3O2S, and the molecular weight is 381.38.

Peak plasma levels are reached 3 hours after fasted oral celecoxib dosing with a half-life of 11 hours. Under fasting conditions, both peak plasma levels (Cmax) and area under the curve (AUC) are roughly dose-proportional up to 200 mg BID; at higher doses there are less than proportional increases in Cmax and AUC. With multiple dosing, steady-state conditions are reached by day five with extensive distribution into tissues and about 97% of the drug protein bound.

Celecoxib metabolism is primarily mediated via CYP2C9 ultimately leading to hepatic elimination. Three metabolites, a primary alcohol, the corresponding carboxylic acid, and its glucuronide conjugate, have been identified in human plasma. These metabolites are inactive as COX-1 or COX-2 inhibitors.

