⁷ Appendix 8: Treating Investigator Patient Assessment Guidance to be filled out by the treating investigator at the time of physical exam.

⁸ See Appendix 8: Treating Investigator Patient Assessment Guidance

⁹ Hematology to include CBC with platelets and differential.

¹⁰ Chemistry to include a complete metabolic panel (CMP).

¹¹ All women of child-bearing potential must have a negative pregnancy test 7 days prior to surgery.

¹² Only required if there is a known history of HIV, hepatitis B, or hepatitis C to confirm eligibility.

¹³ The radiation oncology consultation should be completed prior to registration if possible. This will include a discussion of the indications for adjuvant radiation treatment, a typical treatment course, and the anticipated/possible side effects so the subjects know what to expect if enrolled on trial.

¹⁴ Prior to surgery, the surgical team (physicians, nursing staff, pharmacy, etc.) will be notified about the patients involvement in the trial to ensure standard of care celecoxib and other prohibited therapies are not inadvertently administered.

¹⁵ Patients will complete 1 to 7 days of study therapy prior to surgery and continue twice daily dosing until the last radiation session.

¹⁶ Appendix 3: MDASI Head and Neck Cancer, Appendix 4: EORTC QLQ-H&N43, Appendix 5: Pain Satisfaction Questionnaire, and Appendix 7: Visual Analog Scale for Pain to be completed within 1 month of the scheduled time-points.

¹⁷ Appendix 6: Pre-treatment Questionnaire to be completed at the pre-operation visit.

¹⁸ Patients will be required to record all opioids taken for pain management on Appendix 4: Pain Management Diary while at home. Diary does not need to be maintained during admission post-surgery but should be started when study therapy is started and continue until completion of study therapy.

¹⁹ 5 weeks (\pm 7 days) post-operation the study team will contact the patient to review their medication diary, adverse events, and analgesic use record. If not returning to the study site at this time point, patients will be asked to fax or scan and email their Patient Dosing Diary and Pain Management Diary use records for the study team for review to ensure timely review of study drug compliance.

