10.2 Treatment Period

Once a subject has completed screening, has been found to be eligible, and has been registered, treatment procedures may begin. At the pre-operation visit baseline, questionnaires will be completed and study medication will be dispensed. Patients will be instructed not to begin study medication until 6 days prior to the date of surgery to ensure 5 full days of twice-daily dosing. All pre-operation visit procedures must take place within 14 days prior to surgery unless otherwise noted.

Upon completion of 1 to 7 days of study therapy dosing, patients will undergo head and neck surgery as deemed appropriate by the treating investigator. 14 days (\pm 7 days) after surgery patients will return to the clinic and begin arrangements for adjuvant radiation therapy.

Five to thirty days post-operation every effort should be made to contact the patient to assess study drug compliance and adverse events. For patients not returning to the study site during this time frame, this contact may occur by phone or email. During this contact the study team will check the patient's Dosing Diary, Pain Management Diary, and adverse events. The patient will be asked to scan and email or fax their Dosing Diary and Pain Management Diary for assessment of adherence to the study regimen. However, if the patient does not have access to equipment to do this or is unwilling, failure to obtain the diaries will not be considered a deviation.

During adjuvant radiation, patients will return to clinic for evaluation (Mid-Radiation visit) 5 to 30 days after initiating radiation therapy. Patients will be instructed to continue study therapy twice-daily dosing until completion of their last radiation treatment.

See the Schedule of Events and the Assessments Section for treatment period procedures.

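### Section 7.3.3 sets a different minimum lead-in from the rest of the protocol, and 13.3.2 lets pre-operative dosing exclude a randomised patient whose primary outcome is known

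*Combined protocol and SAP*

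**What the plan says.** On the length of the lead-in, section 7.3.3 (Duration of Therapy) reads: "Subjects will receive twice-daily dosing of 200 mg celecoxib three to seven days prior to surgery". Five other places give a minimum of one day:

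- Study Summary, duration of administration: "Celecoxib/placebo will be taken 1 to 7 days prior to surgery until the completion of adjuvant radiation".
- Section 2.1 (Hypothesis): the same 1 to 7 day start.
- Section 7.1: "Patients will complete 1 to 7 day(s) of study therapy prior to surgery".
- Schedule of Events, footnote 15: "Patients will complete 1 to 7 days of study therapy prior to surgery and continue twice daily dosing until the last radiation session".
- Section 10.2, second paragraph: "Upon completion of 1 to 7 days of study therapy dosing, patients will undergo head and neck surgery".

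The first paragraph of 10.2 also has patients told "not to begin study medication until 6 days prior to the date of surgery to ensure 5 full days of twice-daily dosing". Study drug is dispensed at the pre-operation visit, for which 10.2 says: "All pre-operation visit procedures must take place within 14 days prior to surgery unless otherwise noted". No minimum gap between that visit and surgery is given.

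On who is analysed, section 13.3.2 requires three things for the primary endpoint: a completed lead-in, surgery, and one radiation treatment. It does not say what completing the lead-in means. Section 13.3.1, by contrast, sets a clear threshold of one dose for the toxicity set. Section 12.1 counts the endpoint from surgery as day 0 to the first radiation dose.

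**The concern.** There are two linked problems. The first is operational. If the pre-operation visit falls one or two days before surgery, which 10.2 permits, the resulting lead-in is within protocol under 7.1 and short under 7.3.3. Site staff and monitors cannot tell from the text whether to record a deviation.

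The second concerns the primary analysis. Lead-in dosing takes place after randomisation, and 13.3.2 makes it a condition of entry to the analysis set. The endpoint needs only two dates, and neither depends on pre-operative dosing. No all-randomised set is defined for the primary endpoint, so a patient excluded on this ground is not recovered elsewhere. Because completion is undefined, the discrepancy in 7.3.3 could also be carried into the decision on whether a patient with one or two days of dosing is counted. What is at stake is the avoidable loss of randomised patients whose outcome was observed.

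**Working it through.** **Lead-in statements side by side**

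| Pre-operative dosing | 7.1, Summary, 2.1, footnote 15, 10.2 (second paragraph) | 7.3.3 |
|---|---|---|
| None | Not met | Not met |
| 1–2 days | Met | Not met |
| 3–7 days | Met | Met |

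The conflict is confined to the 1–2 day row. Starting six days before surgery, as the first paragraph of 10.2 intends, satisfies every statement.

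**Endpoint against analysis set**

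The endpoint in 12.1 is the date of first radiation minus the date of surgery. Two of the three conditions in 13.3.2 (surgery, one radiation treatment) are what make this observable. The lead-in condition is not.

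**The plan's own figures**

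Inputs from 13.2: means 72 and 57.2 days, common SD 16.2, 20 per arm, alpha 0.05. The test is taken as two-sided, from 13.4.1. From 4.3: 40 evaluable patients and 25% not starting radiation.

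- Difference: 72 − 57.2 = 14.8 days. Standardised: 14.8 / 16.2 = 0.914.
- Power, two-sample t-test (noncentral t): 0.804, which reproduces the stated 80%.
- Randomised: 40 / 0.75 = 53.3, which reproduces the stated 53.

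The 25% covers only patients who do not start radiation. It makes no allowance for patients who start radiation but fail the lead-in condition.

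**What a lead-in exclusion would cost, by assumption**

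The documents give no rate, so let x be an assumed share of radiation starters who fail the condition. The plan does not settle whether they would be made up: 4.3 targets 40 evaluable patients, but 4.3 and 13.3.2 state replacement only for patients who do not start radiation. Both cases are shown. If patients are made up, the number randomised is 40 / (0.75 × (1 − x)). If not, n per arm is 20 × (1 − x), taking equal loss in both arms.

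| x (assumed) | Randomised to reach 40 | Power if not made up |
|---|---|---|
| 0% | 53.3 | 0.804 (20 per arm) |
| 5% | 56.1 | 0.782 (19 per arm) |
| 10% | 59.3 | 0.759 (18 per arm) |

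If completion means at least one day, x is probably close to zero and the first row applies. The Summary's figure of 60 subjects is not treated here as spare capacity, because it disagrees with the 53 in 4.3.

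**What removing the condition could cost**

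Take an extreme bound in which a share x of analysed active-arm patients gets no benefit at all, with 20 per arm and SD 16.2 unchanged:

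- x = 5%: 14.8 × 0.95 = 14.06 days, power 0.763.
- x = 10%: 14.8 × 0.90 = 13.32 days, power 0.717.

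A patient who merely had a short lead-in and then took study drug up to radiation would lie well inside this bound.

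**The case against.** The strongest reply is that the intended rule is not in doubt. Five statements, including the administration schedule and the schedule of events, say 1 to 7 days, and 7.3.3 stands alone. The protocol also speaks of completing 1 to 7 days in 7.1, footnote 15 and 10.2, and 10.2 places surgery after that completion. On this reading the lead-in condition is nearly implied by having had surgery, and very few patients could be lost. This stands, and it is why the point is minor. It does not remove the need to correct 7.3.3. Nor does it explain why an exclusion the endpoint does not need should remain in 13.3.2.

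It can also be said that a pilot of celecoxib given throughout treatment may reasonably require some pre-operative exposure, and that deleting the condition admits some dilution. This is a fair position. It supports a threshold of one dose, in line with 13.3.1, but not an undefined one.

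Three stronger readings are tempting and not supported:

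- A reader might infer that the start-day instruction in 10.2 is a further contradiction because it bars a start on day −7. It is better read as a target within the window: it aims at five full days of dosing, 3.1.2 says "steady-state conditions are reached by day five", and the next paragraph of 10.2 accepts 1 to 7 days. For the same reason, five days is a weak reading of a completed lead-in.
- A reader might infer outcome-dependent selection between arms. Tolerability could in principle affect lead-in dosing, but the lead-in is short, blinded and over before day 0, and nothing in the documents shows differential exclusion.
- A reader might infer a definite loss of power. Without a rate of incomplete lead-in, none can be claimed.

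**Conclusion.** The point holds as a minor one. Section 7.3.3 conflicts with five other statements for patients with one or two days of pre-operative dosing. Section 13.3.2 permits exclusion of a randomised patient whose primary outcome is known, on a dosing condition that the endpoint does not need. The stated power and number randomised both reproduce and are not in dispute. The size of the effect cannot be computed from the documents. Under the 1 to 7 day reading it is likely near zero. The 5% and 10% rows are illustrations resting on assumed shares, and would matter only if completion were read more strictly or if many patients had no pre-operative dosing.

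**What to change.** 1. In 7.3.3, change the lead-in to 1 to 7 days.
2. In 13.3.2, delete the lead-in condition, so that every randomised patient who has surgery and starts radiation is analysed in the arm assigned. This is still not a full intention-to-treat set, because the surgery and radiation conditions remain.
3. Keep the lead-in condition, with its threshold stated, only for a per-protocol sensitivity analysis, and report days of lead-in by arm (for example 0, 1–2, 3–4, 5–7).
4. If the sponsor insists on an exposure condition in the primary set, state it as at least one dose before surgery.

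The changes should be made before unblinding. They need no new data or visits and leave the 20 per arm and the 53 randomised as they are. The downside is slight dilution from patients with little or no pre-operative dosing. The no-benefit bound would be approached only if the affected patients gained nothing from study drug, for example by never taking it, and the one-dose fallback keeps patients who never took it out of the primary set.
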